6.2 Alcohol, Drug and Tobacco Usage

The number and percentage of subjects with alcohol, drug or tobacco usage status of "current", "previous", or "never" will be summarized by treatment received based on the Safety Set. Within each type of tobacco, the number and percentage of subjects with usage status of "current", "previous", and "never" will be summarized. Type of tobacco includes cigarettes, cigars, pipes, and chewing tobacco.

Alcohol and tobacco usage for the Safety Set will also be included in a data listing containing all subject-level data collected in the eCRF.

6.3 Medical History

A summary for medical history will be presented by body system code and by treatment received based on the Safety Set. If a subject experiences multiple occurrences of medical history of the same body system code, it will be counted only once for that category. Additionally, the number and percentage of subjects with at least 1 medical history will be summarized.

Medical history for the Safety Set will be included in a data listing containing all subject-level data collected in the eCRF.

6.4 Inclusion and Exclusion Criteria

A data listing will be displayed for subjects who did not meet inclusion criteria or subjects who met exclusion criteria for the FAS. Only the inclusion criteria not met and the exclusion criteria met will be listed.

7 Treatments and Medications

7.1 Prior and Concomitant Medications

Use of all concomitant medications that the subject is taking at the time of Visit 1 (Day 1), medications taken up to 14 days prior to Visit 1 (Day 1), and vaccines received 12 months prior to Visit 1 (Day 1) will be collected in the eCRF. All medications will be coded according to the World Health Organization drug dictionary.

A prior medication is defined as any medication that is taken within 12 months prior to the first dose of IP. A concomitant medication is defined as any medication that has a stop date that is on or after the date of first dose of IP. A medication can be considered as both prior and concomitant medication when the start date is before the first dose of IP, but the stop date is on or after the first dose of IP.

Prior medications and concomitant medications will be summarized separately by presenting the number and percentage of subjects having any prior/concomitant medications and having each individual prior/concomitant medication based on Anatomical Therapeutic Chemical (ATC) level 4 and Preferred Term (PT). At each level of subject summarization, a subject is counted once if the subject reported one or more medications. Medications will be sorted in descending order by frequency of ATC level 4 category and preferred terms.

Prior and concomitant medications data collected will be presented in a data listing. A separate listing of concomitant medications collected after Day 142 for the 2-dose vaccination series and Day 262 for the 3-dose vaccination series will be included in the addendum to the CSR once the study is complete.

7.2 Exposure

The number and percentage of subjects who received 1 dose, 2 doses and 3 doses (Groups E, F, K and L only) of IP will be summarized, respectively, based on the Safety Set by treatment received. For the summary of 2 doses and 3 doses of IP, the summary numbers will be presented by doses as randomized and doses different from randomized if detected.

A corresponding listing will be provided with subject-level IP administration details. Also, a listing of subjects with vaccines different from randomized will be provided.

8 Immunogenicity Analysis

Immunogenicity analyses will be performed primarily on IPPS by actual treatment received. IFAS will be the supportive analysis set for immunogenicity analysis based on actual treatments. If HAI or MN titer is undetectable, it will be assigned a value of half the lower limit of detection.

SPR for HAI antibody responses is defined as proportion of subjects achieving a serum HAI titer of at least 1:40 against each vaccine strain in the study. Analysis of SPR for HAI antibody response will be conducted using both IFAS and IPPS.

SCR for HAI or MN antibody responses is defined as proportion of subjects achieving either a prevaccination HAI or MN titer of <1:10 and a postvaccination titer of at least 1:40 or a prevaccination HAI or MN titer of at least 1:10 and a 4-fold or greater increase of HAI or MN postvaccination antibody titers against each vaccine strain in the study. Analysis of SCR and GMTs for HAI or MN antibody responses will be conducted using IPPS only.

A corresponding listing will be provided with individual immunogenicity results per subject, antibody test (HAI or MN), tested strains, and time point based on IFAS.

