7.5 Analysis Sets

The following analysis sets will be used in the statistical analyses.

Full analysis set (FAS): The FAS will consist of all subjects who are randomly assigned to receive IP. All analyses using the FAS will group subjects according to randomized treatment.

Safety set: The safety set will consist of all subjects who are randomly assigned and receive at least 1 dose of IP. Safety endpoint summaries and listings will be performed on the safety set using study group treatment actually received.

Immunogenicity-full analysis set (IFAS): The IFAS will consist of all subjects who are randomly assigned, receive at least 1 dose of IP, and have at least 1 valid postvaccination and

BARDA CSNH5 Influenza Vaccine With Either AS03 or MF59Protocol: BP-I-16-005 Version 2.026 February 2018determinate assay result. As supportive analysis, all the immunogenicity endpoint summarieswill be performed on the IFAS by actual treatments received.

Immunogenicity per-protocol set (IPPS): The IPPS is a subset of the IFAS, where all subjects meet the IFAS criteria and must meet the following criteria:

- have received all the doses of IP to which they were randomly assigned
- have valid and determinate assay result for HAI at Day 43 for Groups A-D and G-J, and Day 163 for Groups E, F, K, L
- have no significant protocol deviations that are determined to potentially interfere with the immunogenicity assessment of IP.

All the immunogenicity endpoint summaries will be performed primarily on the IPPS using treatment actually received.

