3.2.1.2 Primary Immunogenicity Endpoints

SPR (defined as the proportion of subjects achieving a serum HAI titer of at least 1:40 against influenza antigen) against strains contained in the study vaccines on Day 43 for Groups A-D and G-J and on Day 163 for Groups E, F, K and L.

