4.3.2 Full-Analysis Set (FAS)

The FAS will consist of all subjects who are randomly assigned to receive IP. All analyses using the FAS will group subjects according to randomized treatment.

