4.3.4 Immunogenicity-Full Analysis Set (IFAS)

The IFAS will consist of all subjects who are randomly assigned, receive at least 1 dose of IP, and have at least 1 valid postvaccination and determinate assay result. As supportive analysis, all the immunogenicity endpoint summaries will be performed on the IFAS by actual treatments received.

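### SAP Section 8 limits SCR and GMT to the per-protocol set, although SAP 4.3.4 and Protocol 7.5 promise every immunogenicity summary on the IFAS, and SAP 13 does not declare the change

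*SAP*

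**What the plan says.** SAP 4.3.4 defines the IFAS and gives it a role: as supportive analysis, "all the immunogenicity endpoint summaries will be performed on the IFAS by actual treatments received". Protocol 7.5 makes the same commitment, with "As supportive analysis, all the immunogenicity endpoint" summaries to be run on the IFAS by treatment received. Section 8 of the SAP opens consistently with this: the IPPS is primary and the IFAS is the supportive set.

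Section 8 then splits the endpoints. For the primary endpoint it says "Analysis of SPR for HAI antibody response will be conducted using both IFAS and IPPS". For the others it says "Analysis of SCR and GMTs for HAI or MN antibody responses will be conducted using IPPS only". The only IFAS output it leaves for SCR and GMT is a listing of individual HAI and MN results.

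SAP Section 13 names two exploratory objectives that the SAP does not cover. It does not name this restriction.

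**The concern.** The two instructions cannot both be programmed. Whoever builds the tables must choose, and the more specific sentence in Section 8 would probably win. That would remove a summary the protocol promises, with nothing in Section 13 to tell the reader.

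The set matters because every reason for leaving the IPPS arises after randomisation: an assigned dose not received, a dose or sample outside the SAP 4.3.5 windows, or a significant deviation. Some of these may be related to the vaccine. For example, a Grade 3 or higher adverse event that has not resolved or stabilised bars revaccination (footnote p to the schedules of events). The conditions also differ by regimen. Groups E, F, K and L need the Day 142 dose and an in-window Day 163 sample to be in the IPPS, while the two-dose groups need to qualify only through Day 43.

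The MN assay is the most exposed. Its endpoints are titres and SCR only, so under Section 8 it has no supportive summary at all, although two of the four secondary immunogenicity objectives concern MN alone.

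**Working it through.** **Step 1: the plan's own figure.** The only immunogenicity power figures are for SPR against the 70% criterion (SAP Table 4-3, Protocol Table 7-2). With N = 60, the smallest count whose asymptotic 95% lower limit reaches 70% is 49. The exact binomial probability of at least 49 responders at a true SPR of 85% is 81.9%, as stated. The point does not depend on this figure, and the documents give none for SCR, GMT or the share excluded from the IPPS.

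**Step 2: summaries promised and planned.**

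| Endpoint | Protocol 7.5 and SAP 4.3.4 | SAP 8 |
|---|---|---|
| HAI SPR (primary) | IPPS and IFAS | IPPS and IFAS |
| HAI GMT | IPPS and IFAS | IPPS; IFAS listing |
| HAI SCR | IPPS and IFAS | IPPS; IFAS listing |
| MN GMT | IPPS and IFAS | IPPS; IFAS listing |
| MN SCR | IPPS and IFAS | IPPS; IFAS listing |

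Four of the five rows conflict.

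**Step 3: could the SAP be following an older protocol?** SAP Section 1 says it is based on protocol version 1.2. The log for that version (Protocol 12.4.2, change 24), read against the current Section 7.5, shows that this was the version that widened the IFAS role from the primary endpoint to all endpoints. The Section 8 restriction resembles the superseded rule and may be a remnant of it. That is an inference; the documents do not say so.

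**Step 4: what the missing tables could show.** All inputs here are assumptions. Let e be the share of a group in the IFAS but not the IPPS, taken as 5 to 20% (0.05 × 60 = 3 to 0.20 × 60 = 12 subjects if all 60 are in the IFAS).

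SCR gap = IPPS SCR − IFAS SCR = e × (IPPS SCR − SCR in excluded subjects), with IPPS SCR at 85%:

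- Excluded SCR 85%: gap 0.
- Excluded SCR 50%: 0.05 × 35 = 1.75 points, to 0.20 × 35 = 7.0 points.
- Excluded SCR 20%: 0.05 × 65 = 3.25 points, to 0.20 × 65 = 13.0 points.

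GMT ratio, IFAS to IPPS = f^(−e), where excluded subjects' GMT is f-fold lower:

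- f = 2: 2^(−0.05) = 0.97, to 2^(−0.20) = 0.87.
- f = 4: 4^(−0.05) = 0.93, to 4^(−0.20) = 0.76.

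**The case against.** The strongest reply is that little is lost.

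- The primary endpoint keeps its IFAS analysis, and SAP 8.2 plans HAI SPR at every visit.
- For a subject with a prevaccination HAI titre below 1:10, HAI seroconversion and seroprotection are the same event. Prior H5 vaccination or infection is an exclusion criterion, so HAI SPR on the IFAS is probably a close proxy for HAI SCR.
- Individual HAI and MN results are listed on the IFAS.
- The study is descriptive, and at 85% with n = 60 the asymptotic 95% half-width is 1.96 × √(0.85 × 0.15 / 60) = 9.0 points, wider than the 1.75 to 7.0 point gap.
- The IPPS window for the Day 22 dose extends to 10 days late, so modest lateness does not exclude anyone.

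Much of this stands. It narrows the practical gap to MN SCR, GMT for both assays, and HAI SCR in subjects with a baseline titre of 1:10 or more. The proxy argument is itself an inference, since no baseline titres are given, and SPR cannot stand in for a GMT or for MN. A listing is not a summary. The half-width does not settle the matter either: the sets are nested, and the question is selection within the same subjects, not sampling error in one estimate.

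A reader might go further and infer that grouping by actual treatment stops the IFAS from checking the IPPS, or that the IFAS should be grouped as randomised. The documents do not support this. Protocol 7.5 and SAP 4.3.4, 4.3.5 and 8 all state as-treated grouping. Because both sets are grouped the same way, they differ by who is included, which is the contrast of interest. SAP 3.3 keeps subjects who missed a later dose in their randomised group.

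**Conclusion.** The contradiction is real and should be corrected. Section 8 restricts SCR and GMT to the IPPS against SAP 4.3.4 and Protocol 7.5, and Section 13 is silent. As a result, HAI GMT, HAI SCR and all MN endpoints have no planned supportive summary.

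It would be wrong to conclude that the per-protocol result as a whole goes unchecked. The primary result, HAI SPR, is summarised on both sets.

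The textual finding needs no assumption. Its numerical consequence cannot be fixed from the documents. The gap of 1.75 to 7.0 SCR points rests on assumed values for the share excluded, the IPPS SCR and the response in excluded subjects. It could be zero, or up to 13.0 points at an excluded SCR of 20%. The IFAS tables are how a reader would find out.

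**What to change.** Replace the restricting sentence in SAP Section 8 with one that has SCR and GMT, for HAI and MN, summarised on the IPPS as primary and on the IFAS as supportive, both grouped by actual treatment. This brings Section 8 into line with its own opening, SAP 4.3.4 and Protocol 7.5, and no entry in Section 13 is then needed.

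If the sponsor prefers to keep the restriction, SAP 4.3.4 and the opening of Section 8 must be amended and the departure from Protocol 7.5 declared in Section 13. That cures the inconsistency but leaves the secondary endpoints without the check, so it is the weaker repair.

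The cost is a rerun of existing table programs on a set the SAP already defines. Sample size, power and data collection do not change.

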8.1 Primary Analysis

The serum HAI antibody SPR and corresponding asymptotic 95% CIs against the strains contained in the last study vaccines on Day 43 of the prime-boost vaccination series (Groups A-D, G-J) and on Day 163 of the prime-prime-boost vaccination series (Groups E, F, K and L) will be summarized for each treatment group. Bar charts will be presented for SPR.

8.2 Secondary Analysis

- Geometric mean titers (GMTs) of HAI antibody responses against each strain vaccinated at Day 1, 22, 43, and 142 visits (Groups A-D, G-J) and Day 1, 22, 43, 142, 163 and 262 visits (Groups E, F, K and L) and asymptotic 95% CIs will be summarized along with other descriptive statistics, including number of subjects, geometric standard deviation, minimum, maximum, and median for each treatment group. Line plots will be provided for GMT of HAI and corresponding 95% CI for all visits.
- GMTs of MN antibody responses against each strain vaccinated at Day 1, 22, 43, and 142 visits (Groups A-D, G-J) or Day 1, 22, 43, 142, 163 and 262 visits (Groups E, F, K and L) and asymptotic 95% CIs will be summarized along with other descriptive statistics, including number of subjects, geometric standard deviation, minimum, maximum, and median for each treatment group. Line plots will be provided for GMT of MN and corresponding 95% CI for all visits.
- SPR for HAI antibody responses against each strain vaccinated at Day 1, 22, 43, and 142 visits (Groups A-D, G-J) or Day 1, 22, 43, 142, 163 and 262 visits (Groups E, F, K and L) along with asymptotic 95% CIs will be summarized. SPR for the combinations of HAI antibody responses against multiple strains vaccinated will be also summarized for each treatment group. Line plots will be provided for SPR for HAI and corresponding 95% CI for all visits.
- SCR for HAI antibody responses against each strain vaccinated at Day 22, 43, and 142 visits (Groups A-D, G-J) or Day 22, 43, 142, 163 and 262 visits (Groups E, F, K and L) with asymptotic 95% CIs will be summarized for each treatment group. Line plots will be provided for SCR for HAI and corresponding 95% CI for all visits.
- SCR for MN antibody responses against each strain vaccinated at Day 22, 43, and 142 visits (Groups A-D, G-J) or Day 22, 43, 142, 163 and 262 visits (Groups E, F, K and L) with asymptotic 95% CIs will be summarized for each treatment group. Line plots will be provided for SCR for MN and corresponding 95% CI for all visits.

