- 16. Has received an experimental agent (vaccine, biologic, device, blood product, or medication) within 1 month prior to Day 1 (first vaccination) in this study or plans receipt of an experimental agent during the study period.
- 17. Is participating or plans to participate in another interventional clinical study (either active or follow-up phase) during the study period.
- 18. Has received an influenza H5 vaccine in the past or has a history of H5 influenza infection prior to enrollment.
- 19. Has known human immunodeficiency virus, hepatitis B, or hepatitis C infection.
- 20. Has a history of alcohol or drug abuse within 5 years prior to Day 1 (first vaccination).
- 21. Has a body mass index $>35 \text{ kg/m}^2$.
- 22. Has any condition that would, in the opinion of the investigator, place him or her at an unacceptable risk of injury or render him or her unable to meet the requirements of the protocol (including site of injection reactogenicity assessments).
- 23. Is a first-degree relative of any person working on this study: site or sponsor.

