7.7.3 Analysis of Primary Endpoints

7.7.3.1 Analysis of Primary Safety Endpoint

Solicited local and systemic reactions (recorded as AEs, Section 6.2.5.2) during the 8 days after each vaccination, inclusive of the vaccination day, will be summarized as a frequency table that includes 95% exact CIs by study group and by the degree of severity (mild, moderate, or severe).

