8.3 Exploratory Analysis

Exploratory analyses will be performed to compare immunogenicity endpoints between specified study groups. All exploratory analyses will be performed by treatment received based on IPPS. The following group-wise (targeted group vs. reference group) comparisons will be performed for GMT and SPR of HAI antibody responses:

• For strain A/gyrfalcon/Washington/41088-6/2014 H5N8 (Seqirus) on Day 43:

Study Group A vs. Study Group E

Study Group B vs. Study Group E

Study Group C vs. Study Group E

Study Group D vs. Study Group E

Study Group F vs. Study Group E

Study Group G vs. Study Group K

Study Group H vs. Study Group K

Study Group I vs. Study Group K

Study Group J vs. Study Group K

Study Group L vs. Study Group K

 For strain A/barheaded goose/Qinghai Lake/1A/2005 (H5N1) (Sanofi Pasteur) on Day 163: Study Group E vs. Study Group F

Study Group K vs. Study Group L

The logarithms of HAI antibody titers will be compared by two-sided Student's t-test between above specified study groups. Geometric mean ratio estimate will also be presented for each pair of group comparison with corresponding asymptotic 95% CIs and p-values based on two sample t-test.

The difference in proportions (SPR for targeted group-SPR for reference group) between the above specified study groups will be presented along with corresponding asymptotic 95% CIs and p-values based on Chi-square test.

Based on actual results, additional exploratory study group comparisons may be performed.

9 Safety Analysis

All safety evaluations will be performed using the Safety Set.

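### The SPR and SCR confidence intervals are called only asymptotic, with no formula or rule for 0% or 100%; if Wald is used, Day 1 SPR cells of 0 to 3 out of 60 get zero-width or negative limits

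*SAP*

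**What the plan says.** SAP 8.1, on the primary immunogenicity endpoint, plans "The serum HAI antibody SPR and corresponding asymptotic 95% CIs" at Day 43 or Day 163. SAP 8.2 extends this to every sampling visit, including the pre-vaccination one: "or Day 1, 22, 43, 142, 163 and 262 visits (Groups E, F, K and L) along with asymptotic 95% CIs will be summarized". The figures follow the tables: "Line plots will be provided for SPR for HAI and corresponding 95% CI for all visits". The seroconversion rate (SCR) has the same type of interval but starts after vaccination: "SCR for HAI antibody responses against each strain vaccinated at Day 22, 43, and 142 visits". For SPR differences between groups, SAP 8.3 states that they "will be presented along with corresponding asymptotic 95% CIs and p-values based on Chi-square test".

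No section of either document gives the formula, a continuity correction, a truncation rule or a rule for observed rates of 0% or 100%. Protocol 7.7.3.2 and 7.7.4.2 ask for 95% intervals without naming a method.

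The safety proportions are treated differently. Under Protocol 7.7.3.1 the solicited reactions "will be summarized as a frequency table that includes 95% exact CIs by study group", and SAP 9.1 names Clopper-Pearson for them.

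The denominator can be below 60: "Immunogenicity analyses will be performed primarily on IPPS by actual treatment received" (SAP Section 8).

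**The concern.** *Asymptotic* does not identify an interval. Wald and Wilson both qualify and give different limits, so two programmers could follow the SAP faithfully and produce different tables.

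The ordinary reading, particularly next to *exact* in the safety section, is Wald. Wald fails near 0% and 100%, and the SAP plans a table and a line plot where rates near 0% are likely. Day 1 SPR is measured before any study vaccine, and Protocol 4.1.2 excludes anyone who "Has received an influenza H5 vaccine in the past or has a history of H5 influenza infection prior to enrollment". The documents give no baseline titre data, so low Day 1 counts are plausible but not established.

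The SAP plans no formal comparisons for the primary and secondary objectives, so the estimate and its interval are the result. A printed interval of 0 to 0% would claim certainty from about 60 people, and a negative limit is impossible for a proportion.

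**Working it through.** **Inputs.** There are 60 subjects per group (Protocol 7.4, SAP 4.1). The SPR success criterion is 70%, with planned true SPRs of 90, 85 and 80% (Protocol Table 7-2, SAP Table 4-3). Two inputs are assumptions: a per-protocol set of 50 to 60 per group, and true Day 1 rates of 1, 2 and 5%.

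**Does the plan's power table reveal the interval?** Read the criterion as a two-sided 95% lower limit above 70%. Find the smallest count r that meets it, then compute P(X ≥ r) for X ~ Bin(N, p).

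| Rule | r, N=60 | Power at 90 / 85 / 80% | r, N=120 | Power at 90 / 85 / 80% |
|---|---|---|---|---|
| Printed in the plan | – | 98.5 / 81.9 / 44.9 | – | >99.9 / 99.0 / 79.0 |
| Wald | 49 | 98.5 / 81.9 / 44.9 | 93 | >99.9 / 99.0 / 79.0 |
| Wilson | 49 | 98.5 / 81.9 / 44.9 | 94 | >99.9 / 98.1 / 72.1 |
| Clopper-Pearson | 50 | 96.6 / 71.6 / 32.3 | 95 | >99.9 / 96.8 / 64.1 |

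Wald reproduces every printed cell. Wilson fails at N=120 and Clopper-Pearson fails at both sizes. A one-sided 5% exact test also has cut-offs of 49 and 93, so the table supports Wald without proving it.

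**Where Wald breaks down.** The limits are p̂ ± 1.96·√(p̂(1−p̂)/n), with p̂ = x/n. The lower limit is negative, or the width is zero, when x < 3.84/(1 + 3.84/n). That bound is 3.57 at n=50 and 3.61 at n=60, so for every n in that range it means x ≤ 3, and by symmetry x ≥ n−3. For example, 1/60 gives 1.67 ± 1.96·√(0.0167·0.9833/60) = 1.67 ± 3.24 percentage points.

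| Count | Wald (%) | Wilson (%) | Clopper-Pearson (%) |
|---|---|---|---|
| 0/60 | 0 to 0 | 0 to 6.0 | 0 to 6.0 |
| 1/60 | -1.6 to 4.9 | 0.3 to 8.9 | 0.04 to 8.9 |
| 2/60 | -1.2 to 7.9 | 0.9 to 11.4 | 0.4 to 11.5 |
| 3/60 | -0.5 to 10.5 | 1.7 to 13.7 | 1.0 to 13.9 |
| 4/60 | 0.4 to 13.0 | 2.6 to 15.9 | 1.9 to 16.2 |
| 60/60 | 100 to 100 | 94.0 to 100 | 94.0 to 100 |

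At the upper end, 57, 58 and 59/60 give Wald upper limits of 100.5, 101.2 and 101.6%.

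**How often.** P(x ≤ 3 or x ≥ n−3), and exact coverage (the sum of P(X=x) over counts whose interval contains p):

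| True rate | Bad Wald interval, n=60 | Of which 0/60 | Bad Wald interval, n=50 | Wald coverage, n=60 |
|---|---|---|---|---|
| 1% | 99.7% | 54.7% | 99.8% | 45.2% |
| 2% | 96.8% | 29.8% | 98.2% | 70.1% |
| 5% | 64.7% | 4.6% | 76.0% | 80.6% |
| 80% | 0.1% | – | 0.6% | 92.2% |
| 85% | 1.5% | – | 4.6% | 94.4% |
| 90% | 13.7% | – | 25.0% | 94.1% |

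For n from 50 to 60, Wald coverage is 39.5 to 45.2% at a true 1% and 63.5 to 70.1% at 2%. At 5% it is 92.0 to 94.7% for n=50 to 58 and falls to 79.8 to 80.6% at n=59 and 60. The lowest value at the planned SPRs is 87.9% (true 90%, n=50). Over these sizes and all six rates, Wilson covers 89.5 to 98.1% and Clopper-Pearson 95.7 to 99.5%.

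**Differences in SPR (8.3).** Wald coverage at n=60 is mostly acceptable: 99.7% at 1 vs 1%, 93.1% at 5 vs 1%, 94.5% at 90 vs 80%, 92.6% at 90 vs 2%. It is low in isolated cases (82.7% at 98 vs 99%). If both groups are 0/60 or both 60/60, the Wald width is zero, whereas Newcombe gives -6.0 to +6.0 points.

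**The case against.** The best counter-argument is that the harm rests on two things the documents do not settle: that the interval is Wald, and that Day 1 counts are 0 to 3. If Wilson was intended, the boundary problem disappears. Programmers may also truncate limits at 0 and 100%, and no output shells are available to show otherwise. The affected display is a baseline summary in a descriptive study, and individual titres are listed, so a reader could recompute any interval. SCR has no Day 1 cell, nothing in the documents places it near 0% or 100%, and the differences in 8.3 are exploratory. Neither document defines the 70% criterion as a confidence limit, so restating power may be unnecessary.

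Much of this stands as a limit on size. The Wald figures are conditional, the low rates are illustrations, and SCR and the differences are peripheral. It does not remove the point. If Wilson was intended, the SAP still has to say so. Truncation would hide negative limits but would not repair 0 to 0% or the coverage. The power table also fits Wald and not Wilson, though not uniquely.

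**Conclusion.** The concern holds as a minor one. That the interval is unnamed is certain from the text. The defective intervals depend on Wald being used, which is the likelier reading but unproven, and on Day 1 rates near zero, which the eligibility criteria make plausible. Under those assumptions the Day 1 SPR table and plot would often show zero-width or impossible intervals, with coverage far below 95% at true rates of 1 to 2%. The primary SPR table is little affected at the planned 80 to 90% with a full group of 60. It and the SCR tables are exposed only if observed rates fall near 0% or 100%. No decision in the trial changes.

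**What to change.** In SAP 8.1 and 8.2, replace *asymptotic* for SPR and SCR with a named interval: Wilson, or Clopper-Pearson to match SAP 9.1. Either is acceptable. Wilson can dip just below 90% coverage (89.5% at a true 1% with n=55), and Clopper-Pearson is conservative. In 8.3, name Newcombe or Miettinen-Nurminen limits for the SPR differences; this is lower priority.

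State whether the 70% criterion in SAP Table 4-3 and Protocol Table 7-2 means a 95% lower limit above 70%. If it does, restate the power on the chosen interval. Wilson leaves the N=60 column unchanged and lowers N=120 at a true 80% from 79.0 to 72.1%. Clopper-Pearson lowers both columns, for example from 81.9 to 71.6% at N=60 and a true 85%.

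The cost is a few words in the SAP and a SAS option. Restating the power would also mean editing SAP Table 4-3 and Protocol Table 7-2, the latter being a protocol change, and accepting less favourable stated figures.
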